1.2.6 Clinical Experience to Date

Five subjects with thoracic SCI have received AST-OPC1 (formerly GRNOPC1) injections in a previous open-label Phase 1 safety study (Geron Protocol CP35A007). All subjects had a last fully preserved neurological level from T3 – T11 and received a single injection of 2 x 10^6 cells between 7 and 14 days after the injury. Subjects received temporary immunosuppression with tacrolimus, which was tapered at Day 46 of follow up and discontinued at Day 60 per protocol. There were no serious or unexpected adverse events related to AST-OPC1, tacrolimus, or the injection procedure. There were 5 AEs judged to be possibly related to AST-OPC1. One of these AEs was a brief mild elevation of body Amendment 3: 07 July 2017 Confidential Page 23 of 84 temperature. The remaining four AEs all occurred in 1 subject and were primarily neuropathic pain reported as a burning sensation in the trunk and lower extremities. Pain of this type and distribution is also a common complication of SCI.

There were no reports of cyst formation or enlarging masses at the injection sites on MRI scans. All 5 subjects completed 1 year of follow up under protocol CP35A007 and are continuing long-term follow up under a companion protocol, CP35A008. Additional information is provided in the Investigator's Brochure.

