9.3.1 Safety Analyses

All reported adverse events will be coded to a preferred term and classified by System Organ Class using the current version of MedDRA. Adverse events will be listed by subject and will include preferred term, verbatim term, severity, seriousness, relationship, action taken, and outcome. Relationship will address attribution to the investigational product (AST-OPC1), the surgical procedure, and/or the immunosuppressive agent. Tabulations will be prepared for all adverse events, related events, Grade 3 and higher events, and serous events. Designated adverse events of special interest will be tabulated separately as appropriate.

Summary statistics of individual clinical laboratory parameters will be prepared by time period. Shift tables comparing baseline versus most abnormal value will be generated for selected analytes with standard toxicity grades. For selected laboratory analytes, the frequency of abnormal values and/or the incidence of Grades 3 and 4 values may be tabulated if appropriate.

Clinically significant changes in physical examination findings and ECGs will be presented descriptively. Vital signs will be summarized and listed by subject. Findings from immunological assessments will be presented appropriately.

Concomitant medications will be coded to generic term using the World Health Organization Drug Dictionary and will be tabulated across subjects and listed by subject.

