3.2 Study Design

AST-OPC1-01 is an open-label, dose escalation, cross-sequential, multicenter Phase 1/2a study. Subjects with cervical AIS-A SCI will receive 1 of 3 sequential dose levels (2 x 10⁶, 1 x 10⁷ or 2 x 10⁷) of AST-OPC1 injected directly into the spinal lesion within 21 and 42 days after the original injury. Subjects with cervical AIS-B SCI will receive 1 x 10⁷, or 2 x 10⁷ AST-OPC1 cells. All subjects will also receive low-dose tacrolimus for 60 days following injection to prevent immunological rejection. Subjects will be followed for safety and neurologic function for 1 year under this protocol and will then be required to participate in a companion long-term safety follow-up protocol for 14 years. In addition, eligible subjects who were enrolled and had pharmacological deep vein thrombosis (DVT) prophylaxis withdrawn in preparation for surgery, but who never received the AST-OPC1, will be followed for safety for 30 days and assessed separately. All adverse events (AE) will be monitored in an ongoing fashion by the Sponsor's medical monitor and by an independent Data Monitoring Committee.

Page 9 of 33 Confidential

Enrollment in Cohort 1 will be staggered such that there are at least 10 days between administrations of AST-OPC1 to each subject. Enrollment within Cohorts 2-5 will be staggered after the initial subject in each cohort is dosed, with at least 8 days between administration of AST-OPC1 to the first and second subjects. If the first two subjects are successfully dosed with no serious adverse events (SAE) that would trigger study suspension (per the study Suspension Rules), then the remaining subjects in that cohort may be dosed without further staggering.

An additional staggering rule for Cohorts 2-5 is that a minimum of 14 days must elapse between the dosing of any two consecutive subjects who both have a C4 neurological level of injury (NLI). This 14-day stagger for consecutive C4 NLI subjects applies throughout each of these cohorts and also would supersede the 8-day stagger noted above if the first two subjects in any cohort both have a C4 NLI.

Enrollment in Cohort 2 may commence after all three subjects in Cohort 1 have completed 30 days of follow up after AST-OPC1 administration and the safety data for Cohort 1 have been reviewed by the Data Monitoring Committee (DMC).

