6.2.2 Adverse Events

The collection period for adverse events for the purposes of this protocol begins once the subject has signed the informed consent form and ends after 365 days of observation. All adverse events will be listed by subject. The Medical Dictionary for Regulatory Activities (MedDRA) (Version 18) will be used to classify all adverse events by system organ class (SOC) and preferred term (PT).

A treatment emergent adverse event (TEAE) will be considered as any adverse event that starts on or after the date and time of the AST-OPC1 injection, or if an adverse event that started before the AST-OPC1 injection worsened after the administration of the investigational product. For the purposes of determining treatment emergent adverse events, missing or partial AE start dates will be imputed with the following rules:

- 1) If onset date is completely missing, then onset date is set to date of first dose
- 2) If year is present and month and day are missing:
 - a. If year = year of AST-OPC1 dose, then set date to AST-OPC1 dose date
 - b. If year < year of AST-OPC1 dose and medication AE end month and year are available, then set to first of the AE end month
 - c. Otherwise if year < year of AST-OPC1 dose, then set month and day to December 31st.
 - d. If year > year of AST-OPC1 dose, then set month and day to January 1st.
- 3) If month and year are present and day is missing:
 - a. If year = year of AST-OPC1 dose and
 - i. If month = month of AST-OPC1 dose then set day to day of AST-OPC1 dose date

- ii. If month \neq month of AST-OPC1 dose then set day to first day of month
- b. If year \neq year of AST-OPC1 dose then set day to first day of month
- 4) If the AE start date is completely missing and the corresponding stop date is completely missing, the AE start date will remain missing.

A topline summary of treatment emergent adverse events with the number of events, number of subjects, and percentage of subjects for each category below will be tabulated by cohort and overall:

- Any TEAE and SAE
- Subjects Reporting at least one TEAE or TE SAE that has severity Grade 3 or higher that is also related to AST-OPC1, injection procedure, or tacrolimus
- TEAE and SAE Severity: Grade 1/Mild, Grade 2/Moderate, Grade 3/Severe, Grade 4/Life Threatening/Disabling, Grade 5/Fatal
- Categories for TEAE and TE SAE with possible relationship to: AST-OPC1, injection procedure, tacrolimus

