The following tables will be presented for the number and percentage of subjects by cohort and overall:

- TEAE by preferred term sorted by descending number of overall events
- TEAE by SOC, PT, and maximum severity*
- Treatment Emergent Adverse Events by System Organ Class, Preferred Term and Possible Relationship to AST-OPC1, Injection Procedure, and Tacrolimus Treatment emergent SAE by SOC, PT, and maximum severity*
- TEAE of special interest by SOC and PT, defined as Urinary Tract Infections, Spasticity, and Neuropathic Pain based on an adjudication of adverse events by the biostatistics, data management, clinical, and sponsor teams.

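### Events of special interest are assigned by an adjudication that includes the sponsor, in an open-label trial, with no stated term list, case definition, masking, timing or record

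*SAP*

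**What the plan says.** SAP 6.2.2 plans a table of "TEAE of special interest by SOC and PT, defined as Urinary Tract Infections, Spasticity, and Neuropathic Pain", with membership "based on an adjudication of adverse events by the biostatistics, data management, clinical, and sponsor teams". The lead-in to that group of tables is "The following tables will be presented for the number and percentage of subjects by cohort and overall", so this one is split by cohort, that is, by dose and AIS grade. Appendix 9.1 lists it as Table 14.3.2.2 for the All Treated Population.

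The protocol names no special-interest events. Its section 9.3.1 says only "Designated adverse events of special interest will be tabulated separately as appropriate".

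On masking, SAP 3.2 states "AST-OPC1-01 is an open-label, dose escalation, cross-sequential, multicenter Phase 1/2a study". Neither document describes a masked review of adverse events.

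Other parts of the plan bear on this point. All adverse events are coded to MedDRA 18 preferred terms and tabulated by preferred term (SAP 6.2.2). Protocol 9.3.1 adds: "Adverse events will be listed by subject and will include preferred term, verbatim term, severity, seriousness, relationship, action taken, and outcome". SAP 6.2.8 summarizes neuropathic pain separately, from the pain data set.

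**The concern.** Every event already carries a preferred term, so membership of a special-interest group could be settled in advance by a list of terms. The SAP instead leaves it to a judgement by several teams, including the sponsor and the staff who produce the analysis. For a clearly coded event this hardly matters. For a nonspecific one, such as a pain or burning sensation, someone must decide whether it is neuropathic, and no rule is given for that decision.

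The question has some history. In the earlier thoracic trial five events were judged possibly related to AST-OPC1. One was a mild rise in temperature. Of the others, Protocol 1.2.6 says: "The remaining four AEs all occurred in 1 subject and were primarily neuropathic pain". They were reported as a burning sensation, which is the kind of description on which classification can turn.

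What is at stake is the by-cohort pattern in Table 14.3.2.2. If the people deciding know the cohort, or have seen accumulating results, their decisions could create or remove an apparent dose pattern without anyone intending it. SAP 3.2.1 reports that enrolment had closed with 25 subjects treated, so a rule left open can be shaped by data already seen.

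**Working it through.** The plan gives no figure for this point, so there is none to reproduce. The check has two parts.

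**1. What is specified, compared with a similar review in the same SAP.**

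| Feature | Protocol deviation review (SAP 6.1.2) | Special-interest adjudication (SAP 6.2.2) |
|---|---|---|
| Who | Clinical operations, medical, data management and statistics, with sponsor approval | Biostatistics, data management, clinical, sponsor |
| Criteria | Importance defined in words | Three group names only |
| Timing | Before the interim and again before soft lock | Not stated |
| Record | Final decisions documented and kept | Not stated |
| Masking to cohort | Not stated | Not stated |

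The SAP therefore sets timing and a record for one judgement-based review but not for the other. SAP 5.4 has all outputs produced at the interim. If the table is produced again at the final analysis, nothing stated keeps the classification the same on both occasions.

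**2. How far one decision moves the table.**

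Inputs: cohort sizes from SAP 3.2.1, namely 3, 6, 6, 6 and 4. Their sum is 3 + 6 + 6 + 6 + 4 = 25, which matches the stated total.

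The table counts subjects. Moving one subject into or out of a group changes the percentage by 100/n points:

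- Cohort 1: 100/3 = 33.3 points
- Cohorts 2, 3 and 4: 100/6 = 16.7 points each
- Cohort 5: 100/4 = 25.0 points
- Overall: 100/25 = 4.0 points

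The shift occurs only when the reclassified event is the subject's sole event in that group. A subject with another qualifying event is counted either way.

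For example, in Cohort 5 a change from 1/4 to 2/4 moves 25% (exact Clopper-Pearson 95% interval 0.6 to 80.6) to 50% (6.8 to 93.2). The intervals overlap almost entirely, so neither percentage says much about the true rate. A reader of the raw percentages would still see the figure double.

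These are the sizes of a single shift. The documents contain nothing from which to estimate how often an event would be misclassified.

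**The case against.** The case on the other side is substantial, and most of it stands.

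- **Clinicians take part.** The SAP names the clinical team among the adjudicators. It would be wrong to infer that only sponsor and data staff decide.
- **Procedure and knowledge of dose are not stated.** A reader might infer that events are decided one at a time by people who know the dose. The SAP does not say whether the adjudication works on terms or on single events, or what the adjudicators see. Sight of cohort is likely: the design is open label, the sponsor's medical monitor follows all adverse events (Protocol 3.1), and the sponsor is notified at screening to control cohort size and staggering (Protocol 5). It remains an inference.
- **The table is not opaque.** A reader might infer that it cannot be reproduced. The table shows the preferred terms included, all treatment-emergent events are tabulated by preferred term, and the listing gives verbatim terms. Anyone can build a count from the codes. Only the decision on ambiguous terms cannot be re-applied, and that probably matters less for urinary tract infection than for pain or spasticity.
- **Neuropathic pain is not shown to be the product's main known signal.** The four earlier events came from one subject. Protocol 1.2.6 adds that such pain is common after spinal cord injury, and Protocol 1.4.3 names ectopic tissue and teratoma as the potential product risks.
- **There is a separate pain source.** The summaries in SAP 6.2.8 are not tied to this adjudication. They are only a partial substitute: the questionnaire is given at Days 30, 90, 180 and 365 with no baseline (Protocol 7 and 7.14.5), so it cannot establish treatment emergence, and it does not replace the counts for the other two groups.
- **A term list might exist elsewhere.** SAP 6 refers to table shells that are not among the documents, so this cannot be excluded. SAP 7.3.3 does say that derivation algorithms belong in the SAP text rather than in footnotes, and the text has none.
- **A term list does not remove judgement.** A nonspecific code cannot show whether pain is neuropathic, so some manual review will remain. This is correct, and the fix allows for it.

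**Conclusion.** The point holds in limited form and is a cheap improvement. The SAP specifies a method, adjudication by teams that include the sponsor, without the elements that would protect it in an open-label trial. The judgement on ambiguous events is open to bias and cannot be re-applied by a reader. One such judgement can move a cohort percentage by 16.7 to 33.3 points, and the overall figure by 4.0 points.

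A reader might go further and infer that the primary safety result is compromised. The documents do not support that. The tables of incidence, severity, relatedness and serious events do not use this adjudication, no hypothesis is tested (SAP 5.2), and the effect stays within Table 14.3.2.2.

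The conclusion assumes that no term list or adjudication procedure sits in the table shells or another document not provided, and that adjudicators are not masked by some arrangement left unstated.

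**What to change.** Before the interim data cut:

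1. Fix a list of MedDRA 18.0 preferred terms for each of the three groups, and build Table 14.3.2.2 by program from those lists.
2. Limit manual review to nonspecific terms and give it to the clinical team. Use a listing with cohort, dose and relatedness removed and, as far as feasible, subject numbers and dates removed too, because subject identifiers contain a sequential enrolment number (Protocol 5).
3. Document each decision, flag reassigned events in the adverse event listing, and show them in a separate row of the table so that the count from the term list alone stays visible.

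The cost is a short term list and one masked listing; no data collection changes. An oddly coded event may fall outside the list, and the reviewed row is there to catch it. With 25 subjects in sequential cohorts the masking may be incomplete, which should be acknowledged when the table is reported.

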6.2.3 Clinical Laboratory Tests

Summary statistics (N, mean, standard deviation, median, minimum, and maximum) will be tabulated for chemistry, hematology, and liver function laboratory parameters during each period (Screening Visit, Baseline Visit, Post-Injection Days 1-6 Period, Day 7 Visit, Post-Injection Days 8-14 Period, Post-Injection Days 15-21 Period, Post-Injection Days 22-29 Period, Day 30 Visit, Post-Injection Days 31-37 Period, Post-Injection Days 38-44, Post-Injection Days 45-51 Period, Post-Injection Days 52-59 Period, Day 60 Visit, Day 90 Visit, and Day 180 Visit, and Day 365 Visit, as applicable by laboratory parameter) by cohort and overall. N will be calculated as the number of subjects with ≥1 assessment for the given parameter during the period. If a subject has >1 reading during a time period, the mean of the subject's results will be used for the calculation of the mean, SD, and median. For the

^{*}Subjects with >1 AE in respective category will only be counted once. For maximum severity tabulations, subjects will be counted once in the SOC and PT in the maximum severity.

minimum and maximum summary statistics, the minimum and maximum results taken during any assessment within cohort and overall during the time period will be used.

A table counting abnormal flags of the most abnormal value by time period will be generated for each cohort and overall. For each subject, the most abnormal value for a parameter will be taken as the maximum of the absolute value of (lab result – lower reference range) and the absolute value of (lab result – upper reference range) during the time period. At each visit, for each parameter, the number of subjects with low, normal, high, and clinically significant assessments will be tabulated.

Other samples taken, including immune response, xenotransplantation, blood culture, blood glucose, antibodies, and tacrolimus blood level measurement will be listed.

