2. INTRODUCTION

The purpose of this statistical analysis plan (SAP) is to document a more technical and detailed elaboration of the principal features stated in the protocol. This plan includes detail procedure for executing the efficacy analysis for the primary and secondary efficacy endpoints. Further analysis of safety variables (adverse events, clinical laboratory tests, vital signs, AST-OPC1 injection and MRI results) are described in greater detail in this document. Finally, the SAP will reasonably ensure that the tables which will be produced from these analyses, and the data listings, figures, and statistical methodologies that will be used, are complete and allow for the arrival of valid conclusions regarding the study objectives. In the development of this SAP, the following documents and International Conference on Harmonisation of Technical Requirements for Registration of Pharmaceuticals for Human Use (ICH) guidelines were used:

- Protocol AST-OPC1-01, Amendment 3, 07 July 2017
- Electronic Case Report Form (eCRF) Casebook (31 Jul 2017)
- International Conference on Harmonisation (ICH) E3 (1995): Structure and Content of Clinical Study Reports (CSR)
- ICH E6 (R2) (2016): Guideline for Good Clinical Practice
- ICH E9 (1998): Statistical Principles for Clinical Trials

In the event that a discrepancy is found between the descriptions in the statistical section of the protocol and this document, the description in this document supersedes the descriptions in the statistical section of the protocol.

The DP Clinical, Inc. (DPC) Biostatistician is responsible for updating the SAP throughout the life of the study as needed. The responsible party at Asterias will be required to review and approve all versions of the SAP.

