4. STUDY ENDPOINTS AND DEFINITIONS

4.1 Primary Endpoints

The primary endpoint of this Phase 1/2a study is safety and includes observations related to AST-OPC1 cells, the injection procedure, and the protocol-specified immunosuppression regimen. They include:

- Incidence, severity and relatedness of adverse events
- Changes in laboratory variables
- Changes at the injection site as monitored by MRI

Definitions relating to AEs and serious adverse events (SAE) are given in Section 10 of the protocol.

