7.1 Programming Specifications for TLFs

Appendix 1 provides a list of all the TLFs that are planned to be produced.

7.2 Formatting Conventions

The following formatting conventions will be used to output TLFs:

- TLFs are outputted by SAS Output Delivery System (ODS) into Rich Text File (RTF) format.
- Tables and Listings will include borders around all headings and data cells.
- Output will be in landscape orientation with margins of 1.5 inches on top, and 1 inch for right, left, and bottom.
- The default font to be in tables/listings/figures will be Courier New.
- Preferred and minimum font size:

Portion of Output	Preferred	Minimum
Page Header	10 pt	8 pt
Title	10 pt	8 pt
Column header	10 pt	8 pt
Cells	10 pt	8 pt
Footnote	10 pt	8 pt
Page Footer	10 pt	8 pt

- Data will be centered within columns when the maximum length of the data being displayed is less than or equal to the maximum width of the column heading. When the maximum length of the data being displayed exceeds the maximum width of the column heading, the data will be left-justified.
- Column headings should be in initial capital characters. For numeric variables, include "unit" in the column heading when appropriate.
- In figures, axes will be labeled appropriately.

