9. APPENDICES

9.1 Planned Tables, Listings, and Figures

Table Number	Table Name	Population
Table 14.1.1.1	Subject Disposition	Screened Population
Table 14.1.1.2	Reasons for Screen Failures	Screened Population
Table 14.1.2	Demographics	All Treated Population
Table 14.1.3	Medical and Surgical History	All Treated Population
Table 14.1.4	Prior and Concomitant Medications	All Treated Population
Table 14.2.1.1	ISNCSCI Upper Extremity Motor Score and Change	Intent to Treat Population
	from Baseline	•
Table 14.2.1.2.1	ISNCSCI Motor Level and Improvement from Baseline	Intent to Treat Population
Table 14.2.1.2.2	ISNCSCI Sensory Level and Improvement from Baseline	Intent to Treat Population
Table 14.2.2	Spinal Cord Independence Measure III and Changes from Baseline	Intent to Treat Population
Table 14.2.3	GRASSP and Changes from Baseline	Intent to Treat Population
Table 14.3.1.1.1	Topline Summary of Treatment Emergent Adverse Events	All Treated Population
Table 14.3.1.1.2	Topline Summary of Adverse Events Prior to Treatment	Not Treated Population
Table 14.3.1.2	Treatment Emergent Adverse Events by Preferred Term in Descending Order of Total Events	All Treated Population
Table 14.3.1.3	Treatment Emergent Adverse Events by System Organ Class, Preferred Term and Possible Relationship to AST-OPC1, Injection Procedure, and Tacrolimus	All Treated Population
Table 14.3.1.4	Treatment Emergent Adverse Events by System Organ Class, Preferred Term, and Maximum Severity	All Treated Population
Table 14.3.2.1	Treatment Emergent Serious Adverse Events by System Organ Class, Preferred Term, and Maximum Severity	All Treated Population
Table 14.3.2.2	Treatment Emergent Adverse Events of Special Interest	All Treated Population
Table 14.3.4.1.1	Chemistry Laboratory Summary	All Treated Population
Table 14.3.4.1.2	Chemistry Laboratory Result Flags	All Treated Population
Table 14.3.4.1.3	Chemistry Laboratory Results By Subject	All Treated Population
Table 14.3.4.2.1	Hematology Laboratory Summary	All Treated Population
Table 14.3.4.2.2	Hematology Laboratory Result Flags	All Treated Population
Table 14.3.4.2.3	Hematology Laboratory Results By Subject	All Treated Population
Table 14.3.4.3.1	Liver Function Chemistry Laboratory Summary	All Treated Population
Table 14.3.4.3.2	Liver Function Chemistry Laboratory Result Flags	All Treated Population
Table 14.3.4.3.3	Liver Function Laboratory Results By Subject	All Treated Population
Table 14.3.5	Vital Signs Summary	All Treated Population

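### Laboratory change is a primary endpoint component, but the SAP omits the protocol's baseline shift tables, and no planned summary table counts the subjects who worsened from baseline

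*SAP*

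**What the plan says.** SAP 4.1 lists "Changes in laboratory variables" as a component of the primary endpoint, on its own line beside adverse events and MRI. Protocol 9.2.1 does the same.

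For the analysis, Protocol 9.3.1 states: "Shift tables comparing baseline versus most abnormal value will be generated for selected analytes with standard toxicity grades". The protocol names neither the analytes nor the grading scale.

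SAP 6.2.3 plans two kinds of summary for each laboratory parameter, by cohort and overall:

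- N, mean, SD, median, minimum and maximum in each visit or calendar period.
- Flag counts: "A table counting abnormal flags of the most abnormal value by time period will be generated for each cohort and overall". The categories are low, normal, high and clinically significant.

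On completeness, SAP 7.1 says "Appendix 1 provides a list of all the TLFs that are planned to be produced". That list (SAP 9.1) contains flag tables such as "Chemistry Laboratory Result Flags", summary tables, and by-subject result tables for chemistry, hematology and liver function. It contains no laboratory shift table. On precedence, SAP 2 says that where the two documents differ, "the description in this document supersedes the descriptions in the statistical section of the protocol".

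**The concern.** The endpoint is a change, yet neither planned summary measures one. The SAP has the tool: section 4.4.2 defines change from baseline, with baseline as the last assessment before injection. It is applied to the upper extremity motor score (6.3.1), SCIM (6.3.2) and GRASSP (6.3.5), and change is also tabulated for the physical exam (6.2.6). The laboratory endpoint gets none of this. The protocol's shift table is absent, and the SAP gives no reason.

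Two features make the flag counts hard to read as change. First, Protocol 4.2 excludes only creatinine above 1.5 times the limit and AST or ALT above 3 times the upper limit, so a high flag after injection may be a baseline value carried forward. Second, counts by period do not show whether one subject is flagged repeatedly or several are flagged once.

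At stake is a basic descriptive result: for each analyte, how many treated subjects moved from normal to abnormal, or to a worse grade. If the count is made only after the data are seen, the choice of baseline, analytes and grading is made then too, in an open-label study.

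**Working it through.** **Inputs.** Treated subjects (SAP 3.2.1): 3 + 6 + 6 + 6 + 4 = 25, which reproduces the SAP's total. SAP 6.2.3 names 16 laboratory periods. Removing Screening and Baseline leaves 16 − 2 = 14 after injection, and chemistry is scheduled in all of them (Protocol Table 7-1). Of these, 11 run from Days 1-6 to the Day 60 visit; the other three are Days 90, 180 and 365. Hematology is scheduled in 7: Days 1, 7, 30, 60, 90, 180 and 365.

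**What the flag table determines.** Take one analyte and one direction, say high. Let n be the number of subjects, b the number high at baseline, and a₁ … a_K the numbers high in the K later periods. Call a subject newly high if not high at baseline and high in at least one later period. From these counts alone:

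- lower bound = max(0, largest a_k − b)
- upper bound = min(n − b, sum of the a_k)

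The lower bound is reached when flags fall on subjects already high at baseline as far as possible. The upper bound is reached when they fall on different subjects who were not.

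**Numbers.** The documents give no flag counts, so a and b are assumptions, with every subject measured in every period.

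| Setting | n | b | each a_k | K | Newly high |
|---|---|---|---|---|---|
| Chemistry, all follow-up | 25 | 2 | 2 | 14 | 0 to min(23, 28) = 23 |
| Chemistry, through Day 60 | 25 | 2 | 2 | 11 | 0 to min(23, 22) = 22 |
| Chemistry, all follow-up | 25 | 1 | 1 | 14 | 0 to min(24, 14) = 14 |
| Hematology, all follow-up | 25 | 2 | 2 | 7 | 0 to min(23, 14) = 14 |
| Chemistry, one cohort of 6 | 6 | 1 | 1 | 14 | 0 to min(5, 14) = 5 |

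A shift table replaces each range with one exact count. The upper ends require flags to be spread over as many subjects as possible, so they show what the table leaves open and are not forecasts.

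**Period means.** If the same subjects contribute at both times, the difference between a period mean and the baseline mean is the mean change. It does not say how many subjects changed category.

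**The case against.** The strongest reply is that the information is not lost.

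- **By-subject tables.** SAP 9.1 plans three by-subject laboratory tables for the All Treated Population. With 25 subjects, a reader may be able to count shifts by hand.
- **Adverse events.** Protocol 10.1.1 gives a laboratory result that has worsened since baseline as an example of an adverse event. Events so recorded enter the treatment-emergent tables by subject, with severity and possible relationship to tacrolimus (SAP 6.2.2). The earlier thoracic trial reported decreased magnesium this way (Protocol 1.4.4).
- **Flag table content.** It includes a clinically significant category, and Screening and Baseline are among its periods.
- **Weight of the endpoint.** The protocol synopsis states the primary endpoint as related adverse events only, and the study tests no hypotheses.

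Most of this stands as mitigation, but none of it is a planned count of shifts. The table shells are not in the documents, so the layout of the by-subject tables is unknown. The adverse event route depends on the investigator's judgement of clinical relevance (Protocol 10.3), and SAP 4.1 lists laboratory change separately. The clinically significant counts are also per period and not crossed with baseline.

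A reader might go further and infer that the planned tables make it impossible to find how many subjects became abnormal on tacrolimus. The documents do not support that. The by-subject tables together with the tacrolimus administration log (Listing 16.2.4.3.2) may allow a hand count. Nor was an on-tacrolimus period dropped: the protocol's shift table was not tied to exposure, and neither document promised such a period. It may also seem a flaw that "Post-Injection Days 45-51 Period, Post-Injection Days 52-59 Period" cross the taper steps, that "tacrolimus blood level measurement will be listed" and not summarised, or that subjects who stop tacrolimus early stay in later periods. These points do not bear on who became newly abnormal relative to baseline.

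**Conclusion.** The point holds as a reporting gap. A table type that the protocol commits to, for a component of the primary endpoint, is missing from both the SAP text and its list of outputs, and the SAP takes precedence. What remains describes levels and flags period by period. No planned summary table reports the number of subjects newly abnormal or worse than at baseline.

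The size of the gap in this trial cannot be stated, because no flag counts are given; the ranges above rest on assumed counts and complete sampling. The conclusion also assumes that the unseen shells do not already cross flags with baseline, which nothing in SAP 6.2.3 or 9.1 suggests. The underlying data are still collected and shown by subject, so this affects how the result is reported and not whether it can be recovered.

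**What to change.** In SAP 6.2.3 and 9.1, restore the shift table for the All Treated Population, by cohort and overall:

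- Rows: baseline category or toxicity grade, using the last pre-injection value (SAP 4.4.2). Columns: worst post-injection category or grade.
- Show low and high separately, and count each subject once per analyte and direction.
- Cover at least creatinine, potassium, magnesium, AST, ALT and bilirubin. Where grades are used, name the scale.
- Add change from baseline to the period summary statistics.

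Optionally, add a column for the worst value from injection to the last tacrolimus dose. This would be an improvement on both documents, not a restoration.

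The cost is a short SAP edit and one extra table per laboratory group (chemistry, hematology, liver function), from data already collected. No protocol change is needed. It can be in place before the interim analysis planned for September 2018 or, failing that, before the final analysis.
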